13.5 Interim Analyses

After 10 PFS evaluable subjects have been enrolled to the Phase II part of the study, the study will be suspended for a planned interim analysis. The interim analysis will occur 4 months from the tenth evaluable subject's enrollment (unless they have progressed or died first) and will determine if at least 3 of 10 subjects are alive and progression free at 4 months. If the answer is yes, then the study will re-open to accrual and enroll an additional 20 subjects for a total of 30 subjects.

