4 INVESTIGATIONAL PLAN

4.1 Milestone Date Definitions

Registration date: the date the subject signs the informed consent form.

Enrollment date: the date of initiation of study treatment on Cycle 1, Day 1. For the Phase I part of the study, this will be the date of initiation of treatment with carfilzomib, dexamethasone and ruxolitinib. For the Phase II part of the study, this is the date of initiation of treatment with carfilzomib and dexamethasone +/- ruxolitinib.

Treatment discontinuation date: the date the Investigator decides to discontinue the subject from study treatment.

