4.2.2 Phase II Design

Subjects in the Phase II/Run-in period will receive an initial cycle with carfilzomib at the twice weekly dose of 56mg/m² and dexamethasone. Following Cycle 1, a response assessment will be done. Subjects with a response of PR or better (“Responders”) will continue therapy with carfilzomib and dexamethasone. After these responding subjects subsequently progress, they will be treated with ruxolitinib (at the dose established in Phase 1) in combination with carfilzomib and dexamethasone. Subjects with a response of less than PR (“Non-responders”) will add ruxolitinib at the dose established in Phase I to carfilzomib and dexamethasone for all subsequent cycles. The cycle when ruxolitinib is added will be considered Cycle 1 (cycle numbers will start over). Disease evaluation assessment results should be available prior to dosing on Day 1 of each cycle of Phase II until initiation of ruxolitinib treatment (to ensure initiation of ruxolitinib occurs on Day 1 of a cycle).

Enrollment in the Phase II part of the study will be carried out in two stages. During the first stage, 10 PFS evaluable subjects (Section 13.3) will be enrolled. Enrollment and Stage 1 analysis of the first ten subjects on the three drugs (carfilzomib-ruxolitinib-dexamethasone) will be completed to determine if at least 3 of 10 subjects are alive and progression free at 4 months. If so, an additional 20 subjects will be enrolled (a total of 30 subjects) during the second stage. If at least 11 of 30 subjects are alive and progression free at 4 months, the null hypothesis will be rejected (based on binomial probabilities, see Section 13.1.2). The overall duration of the Phase II portion of the study is expected to be no longer than 24 months. For both Phase I and Phase II, subjects will be assessed for response after each cycle with confirmation of response according to IMWG response criteria regardless of dose level treated. Doses of each study drug may be interrupted or reduced in an attempt to manage toxicity.

Table 2: Phase II/Run-In Dosing^a

Drug	Dose	Route	Schedule	Cycle Length
------	------	-------	----------	--------------

Dexamethasone	40 mg ^b	PO	D1, 8, and 15 (Prior to carfilzomib)	28 days
Carfilzomib	56 mg/m ^{2c}	Intravenously (IV) over 30 minutes	D1, 2, 8, 9, 15, and 16	

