^a All subjects enrolled in Phase II will initiate treatment in the Run-in Phase with the exception of subjects who previously received a carfilzomib regimen (prior to study enrollment) of ≥ 56 mg/m². These subjects will proceed directly to Phase II/Ruxolitinib (see Table 3). Subjects will have a disease response assessment prior to Cycle 2 (results must be available prior to Day 1 dosing) and will continue treatment in the Run-In until one of the following:

- Determined to be a “Non-responder” after Cycle 1 (defined as < PR per IMWG criteria) OR
- Determined to be a “Responder” after Cycle 1 (defined as \geq PR per IMWG criteria) with subsequent disease progression

After one of the above criteria are met, subjects will move into the Phase II/Ruxolitinib Phase (see Table 3)

^b A 20 mg dose may be considered for subjects ≥ 75 years of age or for diabetic subjects.

^c Subjects who previously received carfilzomib < 56mg/m² more than 60 days prior to informed consent should receive carfilzomib 20mg/m² on Days 1 and 2 of the first cycle with subsequent doses of 56mg/m²

Table 3: Phase II/Ruxolitinib Dosing^a

Drug	Dose	Route	Schedule	Cycle Length
Dexamethasone	40 mg ^b	PO	D1, 8, and 15 Prior to carfilzomib	28 days *note: Cycle numbers start over at Cycle 1 once ruxolitinib is initiated
Carfilzomib	56 mg/m ²	Intravenously (IV) over 30 minutes	D1, 2, 8, 9, 15, and 16	
Ruxolitinib	MTD from Phase I	PO	Twice daily from C1D1, continuously	

a. Subjects enrolled in Phase II will initiate ruxolitinib at one of the following time-points:

- Initiated treatment in the Run-In Phase and determined to be a “Non-responder” after Cycle 1
- Initiated treatment in the Run-In Phase, determined to be a “Responder” after Cycle 1 with subsequent disease progression
- Determined to have received carfilzomib regimen (prior to study enrollment) of ≥ 56 mg/m². These subjects will skip the Run-In Phase and proceed directly to ruxolitinib (in combination with carfilzomib and dexamethasone).

b. A 20 mg dose may be considered for subjects ≥ 75 years of age or for diabetic subjects

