13.2.2 Primary/Phase II: 4-Month Progression-Free Survival

4-month progression-free survival (PFS4) will be determined for each subject as a binary variable indicating whether or not the subject is alive and progression free at 4 months. The timing of PFS4 begins at the time subjects start treatment with ruxolitinib. The criteria for progression are described in the IMWG Criteria (Appendix [18.3](#)).

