13.3 Analysis Populations

For the Phase I part of the study, the dose escalation and MTD evaluation will be conducted on the population who initiate Cycle 1, Day 1 treatment, and who meet the DLT evaluable criteria as described in Section 4.3. For the Phase II part of the study, the PFS4 evaluable population will include all subjects who initiate treatment with ruxolitinib, have experienced a PFS event within 4 months from the start of ruxolitinib treatment, or have at least 4 months of follow up time from the start of ruxolitinib treatment. The primary efficacy analysis will be conducted on the PFS4 evaluable population. Response-evaluable population will include all subjects (both Phase I and Phase II) who have baseline evaluation, measurable disease, and initiate study

treatment followed by at least one efficacy measurement. All response endpoints will be conducted on the response-evaluable population.

All other efficacy and ruxolitinib safety analyses will be conducted on the population of subjects (both Phase I and Phase II) who initiate treatment with ruxolitinib. Additionally, an analysis will be conducted on safety data collected from Cycle 1 through the cycle prior to initiation of ruxolitinib treatment (for all Phase II subjects initiating Cycle 1 with carfilzomib plus dexamethasone).

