13.4 Analysis Methods

13.4.1 Timing of Analyses

For the Phase I part of the study, an evaluation of the data will take place after each subject completes Cycle 1. For the Phase II part of the study, AESIs will be continuously evaluated in order to assess the Bayesian stopping rules for toxicity described in Section 13.4.3. Additionally, the stage 1 analysis will occur after the first 10 PFS evaluable subjects enrolled have progressive disease, have died, or have at least 4 months of follow up time from ruxolitinib treatment start. The stage 2 analysis will occur after 30 PFS evaluable subjects have progressive disease, have died, or have at least 4 months of follow up time. For both Phase I and Phase II, a follow up analysis will occur when all enrolled subjects have progressed, have died, have become lost to follow up or withdrawn from the study, or have at least two years of follow up time after initiation of treatment with ruxolitinib. A final analysis (for both Phase I and Phase II) will occur when all subjects have died, have become lost to follow up or withdrawn from the study, or have at least 3 years of follow up time after initiation of treatment with ruxolitinib.

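### Section 13.5 times the stage 1 look from the tenth subject's enrollment, Section 13.4.1 from ruxolitinib start; after a run-in, the 13.5 date comes before 4-month status exists

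*Combined protocol and SAP*

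**What the plan says.** Section 13.5 suspends accrual after ten PFS evaluable subjects and sets the date of the look: "The interim analysis will occur 4 months from the tenth evaluable" subject's enrollment, unless that subject has already progressed or died. Accrual re-opens if at least 3 of 10 are alive and progression free at 4 months.

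Enrollment is a defined term. Section 4.1 says: "For the Phase II part of the study, this is the date of initiation of treatment with carfilzomib and dexamethasone +/- ruxolitinib". For a subject who enters the run-in, that is the first day of carfilzomib-dexamethasone.

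Elsewhere the clock starts at ruxolitinib:

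- Section 13.4.1 times the stage 1 analysis when the first ten have progressed, died, or "have at least 4 months of follow up time from ruxolitinib treatment start".
- Section 13.2.2: "The timing of PFS4 begins at the time subjects start treatment with ruxolitinib".
- Section 13.3 admits a subject without an event to the PFS4 evaluable population only with at least 4 months of follow-up from ruxolitinib start.
- Section 4.2.2 speaks of the "Stage 1 analysis of the first ten subjects on the three drugs".

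The run-in is the default route. Note a to Table 2 in Section 4.2.2 reads: "All subjects enrolled in Phase II will initiate treatment in the Run-in Phase with the exception of subjects who previously received" a carfilzomib regimen of at least 56 mg/m². Non-responders add ruxolitinib after one 28-day cycle. Responders wait: "After these responding subjects subsequently progress, they will be treated with ruxolitinib".

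**The concern.** The two sections give different dates for the same decision whenever the tenth subject had a run-in, and the plan does not say which governs. The 13.5 date is the earlier one, by at least one cycle. On that date an event-free tenth subject has not reached the time point that the 3-of-10 rule is about.

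Section 13.5 also follows the tenth subject's clock alone. A run-in responder who enrolled earlier starts ruxolitinib only after progressing, so may reach 4 months later than the tenth subject. Section 13.4.1 covers all ten. In addition, the exception in 13.5 for a subject who has progressed does not specify progression after ruxolitinib start, so a responder's progression during the run-in could be read as meeting it.

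This look is the plan's only efficacy futility stop and decides whether 20 more subjects are enrolled. If an under-followed, event-free subject were scored as a success, an inactive triplet would pass stage 1 more often than designed. If that subject were left out, the rule would be applied to fewer than ten outcomes.

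**Working it through.** **Inputs.** Continue if at least 3 of 10; reject if at least 11 of 30; PFS4 25% under the null (median 2 months) and 50% under the alternative (median 4 months); one-sided alpha 0.10; power at least 90% (Section 13.1.2). Cycle length 28 days (Section 4.2). One month = 30.44 days.

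**1. The design as stated.** Exact two-stage binomial calculation:

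- P(Bin(10, 0.25) ≥ 3) = 0.4744.
- Overall rejection probability: 0.0914 at 25% and 0.9116 at 50%. Both meet the stated targets.
- Expected sample size under the null: 10 + 20 × 0.4744 = 19.49.

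**2. Follow-up on the 13.5 date.** Time since ruxolitinib start = 4 months − run-in length.

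| Run-in (days) | Months on ruxolitinib at the 13.5 date |
|---|---|
| 0 (run-in skipped) | 4.00 |
| 28 (shortest run-in) | 4 − 0.92 = 3.08 |
| 56 | 2.16 |
| 84 | 1.24 |
| 112 | 0.32 |
| 140 | ruxolitinib not yet started |

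The two sections agree only in the first row.

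**3. Effect of counting the tenth subject early.** Assume exponential PFS, which reproduces the conversion in Section 13.1.2: S(t) = 0.5^(t/2) under the null, so S(4) = 0.25 and S(3.08) = 0.344. The tenth subject decides the outcome only when exactly 2 of the other nine succeed: P(Bin(9, 0.25) = 2) = 0.3003.

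- Increase in the pass probability: 0.3003 × (0.3439 − 0.25) = 0.0282.
- Pass probability: 0.4744 + 0.0282 = 0.5026.
- Expected null sample size: 10 + 20 × 0.5026 = 20.05.
- Overall alpha, with true 4-month status used at the final test: 0.0925.

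The documents do not give the share of subjects who have a run-in. If the tenth subject had one with probability q, the pass probability is 0.4744 + 0.0282q: 0.4815 at q = 0.25, 0.4885 at 0.5 and 0.4956 at 0.75.

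**4. Two late subjects affected.** Assume evenly spaced entry and one-cycle run-ins for the latest subjects. The subject enrolled k places before the tenth then has min(4, 3.08 + k/rate) months on ruxolitinib. At each rate below, only the tenth and ninth fall short of 4 months.

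| Accrual per month | Follow-up, tenth / ninth (months) | P(pass), null | Expected null N | Overall alpha |
|---|---|---|---|---|
| 1.25 (30 over 24 months) | 3.08 / 3.88 | 0.5057 | 20.11 | 0.0927 |
| 1.875 (30 over 24 − 4 − 4 = 16 months) | 3.08 / 3.61 | 0.5132 | 20.26 | 0.0929 |
| 2.0 (illustrative) | 3.08 / 3.58 | 0.5142 | 20.28 | 0.0930 |

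The 24 months is the expected overall duration of Phase II in Section 4.2.2. The 16 months takes off a 4-month pause for the look and 4 months of final follow-up.

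**5. Under the alternative.** With only the tenth subject counted early, S(3.08) = 0.5^(3.08/4) = 0.586. The pass probability moves from 0.945 to 0.951, and power from 0.912 to 0.916.

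**The case against.** The strongest reply is that the rest of the plan already prevents the harm. Section 13.5 speaks of evaluable subjects, and 13.3 makes an event-free subject evaluable only if they "or have at least 4 months of follow up time from the start of ruxolitinib treatment". Sections 4.2.2, 13.2.2 and 13.4.1 point the same way. A careful team would probably hold the look until the 13.4.1 date, and a responder still in the run-in could be said not to belong to the first ten on three drugs.

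Much of this stands. The operating-characteristic figures apply only if 13.3 is disregarded, and there is no conflict when the tenth subject skipped the run-in or has already had an event after starting ruxolitinib. Even if the error is made, it is small, and an active regimen is not stopped more often. The accrual rates are assumptions; 2.0 per month has no source in the documents.

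The reply does not repair the date. In 13.5 the 4 months still run from that subject's enrollment, which Section 4.1 defines. Following 13.3 on the 13.5 date leaves fewer than ten outcomes for a rule written for ten. The order in which the ten are chosen is also unsettled, because 13.4.1 refers to evaluable subjects as enrolled while 4.2.2 refers to those on three drugs.

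**Conclusion.** The concern holds. The timing rule in 13.5 is wrong as written for any event-free tenth subject who had a run-in: it falls at least 28 days (0.92 month) before 4-month status exists. It also ignores the other nine subjects' clocks.

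The consequence is an ambiguous date for the futility decision and, if an under-followed subject is miscounted, a modest loss of stopping power. Under the null the chance of continuing rises from 47.4% to 50.3% with one subject affected, and to 50.6–51.4% with two. Expected null sample size rises by 0.6 to 0.8 subject. Overall alpha is at most 0.0930 in these scenarios. These figures rest on exponential PFS, one-cycle run-ins for the affected subjects, and the accrual rates shown. The conflict between the sections needs none of those assumptions. The design itself is sound if 13.4.1 is followed. The correction should be made because it concerns a decision point and costs almost nothing.

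**What to change.** In Section 13.5, replace the enrollment-based timing with the 13.4.1 condition: the look takes place once each of the first ten PFS4 evaluable subjects has, since their own ruxolitinib start, progressed, died or completed at least 4 months of follow-up. Add that no event-free subject with less than 4 months from ruxolitinib start is counted in the 3-of-10 rule. This second sentence repeats what 13.3 implies, but puts it where the decision is made.

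The cost is one or two sentences. When the tenth subject had a run-in, the look comes at least one cycle later than the present 13.5 date, at 4.92 months or more from enrollment if that subject remains event-free. Section 13.4.1 already requires that wait. The 3/10 and 11/30 boundaries, the sample size, alpha (0.0914) and power (0.9116) stay as they are.

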14 STUDY COMPLETION

14.1 Completion

The study will be considered complete when one or more of the following conditions is met:

- All subjects have completed all study visits.
- All subjects have discontinued from the study.

- The IRB, LCI DSMC, Sponsor-Investigator or funding companies discontinue the study because of safety considerations.
- The Sponsor-Investigator defines an administrative or clinical cut-off date.

14.2 Termination

The study will be terminated when one or more of the following conditions occur:

- If risk-benefit ratio becomes unacceptable owing to, for example:
 - Safety findings from this study (e.g. SAEs)
 - Results of any interim analysis
 - Results of parallel clinical studies
 - Results of parallel animal studies (e.g. toxicity, teratogenicity, carcinogenicity or reproduction toxicity).
- If the study conduct (e.g. recruitment rate; drop-out rate; data quality; protocol compliance) does not suggest a proper completion of the trial within a reasonable time frame.

The Sponsor-Investigator has the right to close the trial at any site and at any time.

For any of the above closures, the following applies:

- Closures should occur only after consultation between involved parties.
- All affected institutions must be informed as applicable according to local law.
- In case of a partial study closure, ongoing subjects, including those in follow-up, must be taken care of in an ethical manner.

15 ETHICAL AND LEGAL ISSUES

15.1 Retention of Records

Essential documentation (e.g. adverse events, records of study drug receipt and dispensation), including all IRB correspondence, will be retained for at least 2 years after the investigation is completed. Documentation will be readily available upon request.

15.2 Ethical and Legal Conduct of the Study

The procedures set out in this protocol, pertaining to the conduct, evaluation, and documentation of this study, are designed to ensure that the Investigator abide by Good Clinical Practice (GCP) guidelines and under the guiding principles detailed in the Declaration of Helsinki. The study will also be carried out in keeping with applicable local law(s) and regulation(s).

Documented approval from appropriate agencies (e.g. DSMC, IRB, FDA) will be obtained for all participating centers before start of the study, according to GCP, local laws, regulations and organizations. When necessary, an extension, amendment or renewal of IRB approval must be obtained and forwarded to Amgen and Incyte.

Strict adherence to all specifications laid down in this protocol is required for all aspects of study conduct; the Investigators may not modify or alter the procedures described in this protocol.

Modifications to the study protocol will not be implemented by the Sponsor-Investigator without discussion and agreement by Amgen and Incyte. However, the Investigators may implement a deviation from, or a change of, the protocol to eliminate an immediate hazard(s) to the trial subjects without prior approval from applicable agencies. As soon as possible, the implemented deviation or change, the reasons for it and if appropriate the proposed protocol amendment should be submitted to the appropriate agencies. Any deviations from the protocol must be explained and documented by the Investigator. If a deviation occurs, the event should be reported to the Sponsor-Investigator promptly. Any IRB reportable event that occurs must be reported to the IRB per IRB requirements. All planned (intentional) deviations must be submitted to the Sponsor-Investigator for approval prior to implementation or planned occurrence. After Sponsor approval has been obtained, planned deviations must be submitted and approved by the IRB prior to the anticipated deviation occurring. Exceptions for eligibility criteria are not allowed.

The Sponsor-Investigator is responsible for the conduct of the clinical trial at the sites in accordance with Title 21 of the Code of Federal Regulations and/or the Declaration of Helsinki. The Sponsor-Investigator is responsible for personally overseeing the treatment of all study subjects. The Sponsor-Investigator must assure that all study site personnel, including sub-investigators and other study staff members, adhere to the study protocol and all applicable regulations and guidelines regarding clinical trials both during and after study completion.

The Sponsor-Investigator will be responsible for assuring that all the required data will be collected and properly documented.

15.3 Confidentiality

All records identifying the subject will be kept confidential and, to the extent permitted by the applicable laws and/or regulations, will not be made publicly available.

16 PUBLICATION POLICY

The Sponsor-Investigator must send a draft manuscript of the publication or abstract to Amgen and Incyte prior to submission of the final version for publication or congress presentation. All relevant aspects regarding data reporting and publication will be part of the contract between Amgen, Incyte and the Sponsor-Investigator.

The Sponsor-Investigator will ensure that the information regarding the study be publicly available on the internet at www.clinicaltrials.gov.

18 APPENDICES

18.1 ECOG Performance Scale

Grade	Description
0	Normal activity, fully active, able to carry on all pre-disease performance without restriction.
1	Symptoms, but fully ambulatory, restricted in physically strenuous but ambulatory and able to carry out work of a light or sedentary nature (e.g. light housework, office work).
2	Ambulatory and capable of all self-care but unable to carry out any work activities. Up and about more than 50% of waking hours.
3	Capable of only limited self-care, confined to bed or chair more than 50% of waking hours.
4	Completely disabled. Cannot carry on any self-care. Totally confined to bed or chair.
5	Dead

18.2 NCI CTCAE VERSION 4.03

Common Terminology Criteria for Adverse Events (CTCAE) of the National Cancer Institute (NCI) v4.03

Publish Date: (v4.03: June 14, 2010)

http://evs.nci.nih.gov/ftp1/CTCAE/CTCAE_4.03_2010-06-14_QuickReference_8.5x11.pdf

18.3 Response Criteria for Multiple Myeloma

IMWG Response Criteria*

IMWG MRD Criteria (Requires a complete response as defined below)	
Sustained MRD-negative	MRD negativity in the marrow (NGF or NGS, or both) and by imaging as defined below, confirmed minimum of 1 year apart. Subsequent evaluations can be used to further specify the duration of negativity (eg, MRD-negative at 5 years)†
Flow MRD-negative	Absence of phenotypically aberrant clonal plasma cells by NGF‡ on bone marrow aspirates using the EuroFlow standard operation procedure for MRD detection in multiple myeloma (or validated equivalent method) with a minimum sensitivity of 1 in 10 ⁵ nucleated cells or higher
Sequencing MRD-negative	Absence of clonal plasma cells by NGS on bone marrow aspirate in which presence of a clone is defined as less than two identical sequencing reads obtained after DNA sequencing of bone marrow aspirates using the LymphoSIGHT platform (or validated equivalent method) with a minimum sensitivity of 1 in 10 ⁵ nucleated cells§ or higher
Imaging-positive MRD-negative	MRD negativity as defined by NGF or NGS plus disappearance of every area of increased tracer uptake found at baseline or a preceding PET/CT or decrease to less mediastinal blood pool SUV or decrease to less than that of surrounding normal tissue¶
Standard IMWG Response Criteria ; NOTE: see [28] for additional details	
Stringent Complete Response (sCR)	
 Complete response as defined below plus normal FLC ratio** and absence of clonal cells in bone marrow biopsy by immunohistochemistry (κ/λ ratio $\leq 4:1$ or $\geq 1:2$ for κ and λ patients, respectively, after counting ≥ 100 plasma cells)††
Complete Response (CR)	
 Negative immunofixation on the serum and urine and disappearance of any soft tissue plasmacytomas and $<5\%$ plasma cells in bone marrow aspirates. In patients with only FLC disease, a normal FLC ratio of 0.26–1.65 is required.
Very Good Partial Response	
 Serum and urine M-protein detectable by immunofixation but not on electrophoresis or $\geq 90\%$ reduction in serum M-protein plus urine M-protein level <100 mg

(VGPR)	per 24 h
Partial Response (PR)	
 • $\geq 50\%$ reduction of serum M-protein plus reduction in 24 h urinary M-protein by $\geq 90\%$ or to < 200 mg per 24 h; • If the serum and urine M-protein are unmeasurable, a $\geq 50\%$ decrease in the difference between involved and uninvolved FLC levels is required in place of the M-protein criteria; • If serum and urine M-protein are unmeasurable, and serum-free light assay is also unmeasurable, $\geq 50\%$ reduction in plasma cells is required in place of M-protein, provided baseline bone marrow plasma-cell percentage was $\geq 30\%$. In addition to these criteria, if present at baseline, a $\geq 50\%$ reduction in the size (SPD)§§ of soft tissue plasmacytomas is also required
Minimal Response (MR)	
 • $\geq 25\%$ but $\leq 49\%$ reduction of serum M-protein and reduction in 24-h urine M-protein by 50–89%. In addition to the above listed criteria, if present at baseline, a $\geq 50\%$ reduction in the size (SPD)§§ of soft tissue plasmacytomas is also required.
Stable Disease (SD)	
 • Not recommended for use as an indicator of response; stability of disease is best described by providing the time-to-progression estimates • Not meeting criteria for CR, VGPR, PR, MR or progressive disease
Progressive disease (PD)¶¶,	
Increase of $\geq 25\%$ from lowest response value in any one or more of the following:
 
 • Serum M-protein (absolute increase must be ≥ 0.5 g/dL); • Serum M-protein increase ≥ 1 g/dL, if the lowest M component was ≥ 5 g/dL; • Urine M-protein (absolute increase must be ≥ 200 mg/24 h); • In patients without measurable serum and urine M-protein levels, the difference between involved and uninvolved FLC levels (absolute increase must be > 10 mg/dL); • In patients without measurable serum and urine M-protein levels and without measurable involved FLC levels, bone marrow plasma-cell percentage irrespective of baseline status (absolute increase must be $\geq 10\%$); • Appearance of a new lesion(s), $\geq 50\%$ increase from nadir in SPD§§ of > 1 lesion, or $\geq 50\%$ increase in the longest diameter of a previous lesion > 1 cm in short axis; • $\geq 50\%$ increase in circulating plasma cells (minimum of 200 cells per μL) if this is the only measure of disease 
‡

Clinical Relapse	
Clinical relapse requires one or more of the following criteria:
 
 • Direct indicators of increasing disease and/or end organ dysfunction (CRAB features) related to the underlying clonal plasma-cell proliferative disorder. It is not used in calculation of TTP or PFS but is listed as something that can be reported optionally or for use in clinical practice; • Development of new soft tissue plasmacytomas or bone lesions (osteoporotic fractures do not constitute progression); • Definite increase in the size of existing plasmacytomas or bone lesions. A definite increase is defined as a 50% (and ≥ 1 cm) increase as measured serially by the SPD§§ of the measurable lesion; • Hypercalcaemia (> 11 mg/dL);

- Decrease in haemoglobin of ≥ 2 g/dL not related to therapy or other non-myeloma-related conditions;
- Rise in serum creatinine by 2 mg/dL or more from the start of the therapy and attributable to myeloma;
- Hyperviscosity related to serum paraprotein

For MRD assessment, the first bone marrow aspirate should be sent to MRD (not for morphology) and this sample should be taken in one draw with a volume of minimally 2 mL (to obtain sufficient cells), but maximally 4–5 mL to avoid haemodilution. IMWG=International Myeloma Working Group. MRD=minimal residual disease. NGF=next-generation flow. NGS=next-generation sequencing. FLC=free light chain. M-protein=myeloma protein. SPD=sum of the products of the maximal perpendicular diameters of measured lesions. CRAB features=calcium elevation, renal failure, anaemia, lytic bone lesions. FCM=flow cytometry. SUV_{max} =maximum standardised uptake value. MFC=multiparameter flow cytometry. ^{18}F -FDG PET= ^{18}F -fluorodeoxyglucose PET. ASCT=autologous stem cell transplantation.

* All response categories require two consecutive assessments made any time before starting any new therapy; for MRD there is no need for two consecutive assessments, but information on MRD after each treatment stage is recommended (e.g., after induction, high-dose therapy/ASCT, consolidation, maintenance). MRD tests should be initiated only at the time of suspected complete response. All categories of response and MRD require no known evidence of progressive or new bone lesions if radiographic studies were performed. However, radiographic studies are not required to satisfy these response requirements except for the requirement of FDG PET if imaging MRD-negative status is reported. †Sustained MRD negativity when reported should also annotate the method used (e.g., sustained flow MRD-negative, sustained sequencing MRD-negative).

‡ Bone marrow MFC should follow NGF guidelines.³⁰ The reference NGF method is an eight-colour two-tube approach, which has been extensively validated. The two-tube approach improves reliability, consistency, and sensitivity because of the acquisition of a greater number of cells. The eight-colour technology is widely available globally and the NGF method has already been adopted in many flow laboratories worldwide. The complete eight-colour method is most efficient using a lyophilised mixture of antibodies which reduces errors, time, and costs. 5 million cells should be assessed. The FCM method employed should have a sensitivity of detection of at least 1 in 10^5 plasma cells.

§ DNA sequencing assay on bone marrow aspirate should use a validated assay such as LymphoSIGHT (Sequentia).

¶ Criteria used by Zamagni and colleagues,⁸⁵ and expert panel (IMPetUs; Italian Myeloma criteria for PET Use).^{81,97} Baseline positive lesions were identified by presence of focal areas of increased uptake within bones, with or without any underlying lesion identified by CT and present on at least two consecutive slices. Alternatively, an $SUV_{max}=2.5$ within osteolytic CT areas >1 cm in size, or $SUV_{max}=1.5$ within osteolytic CT

areas ≤ 1 cm in size were considered positive. Imaging should be performed once MRD negativity is determined by MFC or NGS.

|| Derived from international uniform response criteria for multiple myeloma.¹¹ Minor response definition and clarifications derived from Raj Kumar and colleagues.¹⁴ When the only method to measure disease is by serum FLC levels: complete response can be defined as a normal FLC ratio of 0.26 to 1.65 in addition to the complete response criteria listed previously. Very good partial response in such patients requires a $\geq 90\%$ decrease in the difference between involved and uninvolved FLC levels. All response categories require two consecutive assessments made at any time before the institution of any new therapy; all categories also require no known evidence of progressive or new bone lesions or extramedullary plasmacytomas if radiographic studies were performed. Radiographic studies are not required to satisfy these response requirements. Bone marrow assessments do not need to be confirmed. Each category, except for stable disease, will be considered unconfirmed until the confirmatory test is performed. The date of the initial test is considered as the date of response for evaluation of time dependent outcomes such as duration of response.

** All recommendations regarding clinical uses relating to serum FLC levels or FLC ratio are based on results obtained with the validated Freelite test (Binding Site, Birmingham, UK).

†† Presence/absence of clonal cells on immunohistochemistry is based upon the $\kappa/\lambda/L$ ratio. An abnormal κ/λ ratio by immunohistochemistry requires a minimum of 100 plasma cells for analysis. An abnormal ratio reflecting presence of an abnormal clone is κ/λ of $>4:1$ or $<1:2$.

‡‡ Special attention should be given to the emergence of a different monoclonal protein following treatment, especially in the setting of patients having achieved a conventional complete response, often related to oligoclonal reconstitution of the immune system. These bands typically disappear over time and in some studies have been associated with a better outcome. Also, appearance of monoclonal IgG κ in patients receiving monoclonal antibodies should be differentiated from the therapeutic antibody.

§§ Plasmacytoma measurements should be taken from the CT portion of the PET/CT, or MRI scans, or dedicated CT scans where applicable. For patients with only skin involvement, skin lesions should be measured with a ruler. Measurement of tumour size will be determined by the SPD.

¶¶ Positive immunofixation alone in a patient previously classified as achieving a complete response will not be considered progression. For purposes of calculating time to progression and progression-free survival, patients who have achieved a complete response and are MRD-negative should be evaluated using criteria listed for progressive disease. Criteria for relapse from a complete response or relapse from MRD should be used only when calculating disease-free survival.

|||| In the case where a value is felt to be a spurious result per physician discretion (eg, a possible laboratory error), that value will not be considered when determining the lowest value.

